5.2. Data collection

Hospitals participating in the study will proactively gather data from all surgical procedures involving patients in a consecutive manner, under the supervision of the local investigator. All data collected are integral to standard clinical care. A visual representation of the trial's design can be found in Figure 2.

Patient characteristics: information such as baseline characteristics and preoperative risk factors essential for identifying patients prone to PPCs. This includes details like age, gender, height, weight, predicted body weight, smoking status, comorbidities, preoperative biochemical exams, peripheral oxygen saturation (SpO2), frailty scale, and American Society of Anesthesiologists (ASA) score. Additionally, data on the type and indication for surgery will be gathered for computing the Assess Respiratory Risk in Surgical Patients in Catalonia (ARISCAT) and Revised Cardiac Risk Index (RCRI). Surgical characteristics: urgency degree of surgery (emergent vs urgent vs elective procedure), planned duration of surgery, type of surgical procedure, and surgical technique.

Operator characteristics: gender, years of anesthesiologist practice, and experience in critical care.

Center characteristics: academic vs non-academic, grade of workload.

Data collection on day 0: type of anesthesia (volatile anesthetic medications or intravenous agents); IMV settings and monitored parameters will be intra-operatively collected at induction and hourly including ventilatory mode, peak inspiratory pressure (cmH₂O), plateau pressure (cmH₂O) (if available), inspiratory to expiratory ratio (I/E), and plateau time (seconds or %), mean airway pressure (cmH₂O), actual inspired tidal volume (Vt) (ml), applied positive end-expiratory pressure (PEEP) and total PEEP with any intrinsic PEEP (cmH₂O) (if present), respiratory rate (breaths/min), dynamic and static respiratory system compliance (cmH₂O/ml) (if clinically available); airway

resistance (Raw) (cmH₂O/(l/sec)) (if clinically available), inspired oxygen fraction (FiO₂), use of recruitment maneuvers (number and type), peripheral oxygen saturation (SpO₂) (%), end-tidal carbon dioxide tension (EtCO₂) (mmHg or kPa), mean, systolic, and diastolic arterial pressure (either invasive or non-invasive) (mmHg), heart rate (beats per minute), body temperature (°C) (if assessed), and arterial blood gases analysis (if present).

Weaning phase: at beginning and at the end of weaning phase, the following variables will be acquired: ventilatory mode, Vt (ml), PEEP (cmH₂O), pressure support over PEEP (if any) (cmH₂O), inspiratory trigger regulations, FiO₂, respiratory rate (breaths/min), SpO₂ (%), EtCO₂(mmHg or kPa), mean, systolic, and diastolic arterial pressure (either invasive or non-invasive), mmHg, heart rate (beats per minute).

It will also be recorded if aspiration is performed prior to tube removal. The number and type of IAEs will be acquired throughout the whole duration of surgical and anesthesiologic procedures (see "11" for definitions).

Peri-operative variables: duration of anesthesia procedure, duration of surgical procedure, tube type and size, type of anesthesia, type of analgesia (total endovenous, antibiotic prophylaxis, details on neuromuscular function monitoring and about the use of reversal agents (if any), total intra-operative fluid and total transfusion of blood products, temperature and hemoglobin at end of surgery (if clinically available). The possible admission to post-anesthesia care unit (PACU) and the eventual administration of non-invasive respiratory support (NIRS), namely, high flow oxygen therapy, continuous positive airway pressure, and non-invasive bilevel positive airway pressure ventilation, and the settings will be recorded.

Post-operative variables: vital signs involving SpO₂, heart rate, systolic, diastolic, and mean arterial pressure, body temperature if assessed, eventual arrythmias occurrence, and the blood gas analysis parameters (optional assessment) will be hourly collected in the immediate post-operative period or PACU stay, and at the discharge to surgical ward or ICU.

Follow up (day 0 to 5): PPCs are recorded from the medical chart on day 0 (end of surgery to 23:59h) and on days 1,2,3,4 and 5 post-operative (each day runs from 00:00 AM to 23:59 PM). Follow–up is completed on the day of discharge or on day 5 if the patient is still admitted.

On day 0 the following variables are collected: IMV after discharge from the operation room, admission to ICU/PACU after surgery, PPCs (see "11").

On day 1,2,3,4 and 5 the following variables will be collected: any new admission to ICU; any new or prolonged IMV; PPCs (see "11").

The data mentioned above are considered essential to defined as "complete" each patient's medical record.

ICU or PACU admission: recording of data during the critical care submission can be left out by the participating centers if this workload exceeds their possibilities. However, it is requested to collect the ICU/PACU data. In case of IMV and/or admission to the ICU/PACU during the follow-up period (day 0, 1, 2, 3, 4 or 5), the following variables will be collected on a different CRF: reason for ICU/PACU admission, reason for IMV or NIRS, APACHE II score (24), on (first) admission to and within the first 24 hours in ICU (i.e., the APACHE II score to be collected and reported for patients who were in the ICU before surgery, and were referred to the ICU after surgery, starts direct after the first admission to the ICU; the APACHE II score to be collected and reported for patients who were not in the ICU before surgery, but were referred to the ICU after surgery, starts direct after surgery, in the ICU). At the first hour of ICU/PACU admission and in case of continued admission each day (during morning rounds) the following variables are collected: SOFA score, IMV regulations, arterial blood gas values (pH, PaCO₂, PaO₂ if available), closest to 08:00 AM, PPCs (number and type, see "p 11"), extra-pulmonary organ failure (number and type), and risk factors for respiratory failure (number and type).

If a patient is transferred back to the ward, the non–ICU/PACU follow–up CRF will be used to record the variables of the remaining follow–up days.

Follow up (day 28): On day 28 ICU and hospital length of stay as well as in hospital death are assessed.

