2. HYPOTHESYS AND OBJECTIVES

2.1. Study hypothesis

PPCs incidence is high and related to patient and surgery characteristics. The key mechanical ventilator regulations during general anesthesia for surgery are independently associated with PPCs incidence. Finally, postoperative outcomes is strongly conditioned by PPCs occurrence.

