4.2. Inclusion criteria

Patients are eligible if:

- adults:
- receiving intraoperative IMV (via tracheal intubation, or supraglottic device) during general anesthesia for surgery.

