4.3. Exclusion criteria

The following patients will be excluded:

- subjected to IMV outside of an operating room; and
- subjected to IMV during extracorporeal life support.

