5.1.2. Secondary outcomes

Secondary endpoints include: 1) ascertaining the practice of mechanical ventilation in patients undergoing general anesthesia for surgery including key intraoperative ventilator characteristics and respiratory system mechanics; 2) describing the incidence and type of IAEs; 3) describing postoperative complications other than PPCs in the first 5 postoperative days or hospital discharge whichever comes first; 4) describing the impact of intraoperative hemodynamic management on the occurrence of PPCs; 5) reporting intensive care unit (ICU) admission and length of stay, hospital length of stay, and hospital mortality on day 28.

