6. STATISTICAL ANALYSIS

The demographic and baseline characteristics of the study population will be reported. Continuous variables will be summarized using median and interquartile range (IQR), and categorical variables will be summarized using frequencies and percentages. The comparison among groups for categorical variables will be performed by considering the Chi-square test or Fisher's exact test whatever is appropriate; for continuous variables, the Wilcoxon -Rank Sum test will be used.

The primary endpoint, namely, the PPCs rate, will be calculated together with the 95% confidence interval (CI). Moreover, the impact of the patient's characteristics on the risk of PPCs will be handled by using appropriate statistical models, such as Logistic Regression. These analyses will be adjusted for potential confounders identified at the study's outset, providing insights into factors that may influence PPCs rates among the patients population subjected to surgery. The 95% CIs on the model OR (Odds Ratios) and predicted probability of PPCs, according to the patient's profile, will be estimated. Handling of missing data will be addressed through robust methods like multiple imputation or complete case analysis, depending on the nature and extent of the missingness. Sensitivity analyses will further assess the robustness of the findings, examining how different assumptions about the missing data and analytical methods influence the results.

The significance of differences will be defined by the p-values, with a value of less than 0.05 considered statistically significant.

The following planned secondary analyses will be performed:

- Cardiac vs non-cardiac surgery
- Elective vs non-elective procedures
- Obese vs non-obese patients
- Open vs minimally invasive/robotic surgery

- Comparison among the different obesity classes
- Practice of weaning from invasive mechanical ventilation
- Impact of geo-economical difference

The analyses will be performed by using R 3.4.2.

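### In cases that end before the first hourly reading, airway pressures (other than applied PEEP) and respiratory mechanics are recorded only at induction

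*Protocol*

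**What the plan says.** Section 5.2 (Data collection) sets the intraoperative schedule: "IMV settings and monitored parameters will be intra-operatively collected at induction and hourly including ventilatory mode". The list that follows covers peak, plateau and mean airway pressure, I/E ratio, tidal volume, applied and total PEEP, respiratory rate, compliance, resistance, FiO2 and monitored vital parameters. Plateau pressure, compliance and resistance are requested only where available, and total PEEP where intrinsic PEEP is present.

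The same section adds a second, shorter record: "Weaning phase: at beginning and at the end of weaning phase, the following variables will be acquired: ventilatory mode, Vt (ml), PEEP". It continues with pressure support, trigger, FiO2, respiratory rate, SpO2, EtCO2 and haemodynamics.

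Eligibility in section 4.2 is for adults "receiving intraoperative IMV (via tracheal intubation, or supraglottic device) during general anesthesia for surgery". Section 4.3 excludes only ventilation outside an operating room and ventilation during extracorporeal life support. Neither section mentions length of surgery or ventilation.

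Secondary endpoint 1 (section 5.1.2) is "ascertaining the practice of mechanical ventilation in patients undergoing general anesthesia for surgery including key intraoperative ventilator characteristics and respiratory system mechanics". Section 6 plans a comparison of open with minimally invasive or robotic surgery.

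**The concern.** The endpoint is meant to describe ventilation and mechanics during surgery. In a short operation, the only scheduled look at most pressures and at all mechanics comes at the start of anaesthesia. Positioning and gas insufflation ordinarily follow induction, so an induction value can miss their effect. The protocol gives this effect as a reason for the study: the Summary points to extreme body positions in minimally invasive and robotic procedures, and section 1.1 says that steep head-down positioning can alter ventilatory characteristics considerably.

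If short minimally invasive cases contribute only induction values, a comparison of their mechanics with open surgery partly compares patients before the exposure of interest has begun. This is a gap in what is collected. Each hospital collects data for one week, and a value not entered then cannot be restored in the analysis.

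**Working it through.** **The plan's own figure.** The only calculated figure in the protocol is the confidence interval width of 0.0119 in section 4.4. Clopper-Pearson limits for 1,000 events in 10,000 patients at 95% give a width of 0.01186, which rounds to 0.0119. The figure reproduces, and this point does not depend on it.

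**Step 1: items by record.** The two lists in section 5.2, side by side:

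| Items | Induction and hourly record | Weaning record (beginning, end) |
|---|---|---|
| Mode, tidal volume, applied PEEP, FiO2, respiratory rate | listed | listed |
| SpO2, EtCO2, arterial pressures, heart rate | listed | listed |
| Peak, plateau and mean airway pressure | listed (plateau if available) | not listed |
| I/E ratio, total PEEP | listed (total PEEP if present) | not listed |
| Compliance, resistance | listed (if available) | not listed |

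**Step 2: readings by case length.** The protocol does not define the hourly clock. Assume that it starts at the induction reading. For a case of d minutes:

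- scheduled full-set readings = 1 + floor(d/60)
- of these, readings after induction = floor(d/60)

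| d (minutes) | Full-set readings | After induction |
|---|---|---|
| 20, 30, 45, 59 | 1 | 0 |
| 60, 90 | 2 | 1 |
| 120 | 3 | 2 |
| 240 | 5 | 4 |

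**Step 3: a case under one hour.** Items in the first two rows of the first table have up to 1 + 2 = 3 readings (induction, beginning of weaning, end of weaning). Items in the last three rows have 1 + 0 = 1, at induction. Where plateau pressure, compliance or resistance is not available at that moment, they have none.

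**Step 4: how many patients.** The documents give no distribution of case length, so the share s under one hour is unknown. At the planned size the affected number is 10,000 × s, so each percentage point is 10,000 × 0.01 = 100 patients. The share is unlikely to be zero: enrolment is consecutive, there is no minimum duration, and supraglottic-device cases are eligible.

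**Step 5: other records.** Section 5.2 collects intraoperative adverse events over the whole procedure, and section 11.2 counts measures to lower airway pressure and expiratory flow limitation among them. A short case can therefore show that such an event occurred, but not the pressure or compliance at the time.

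**The case against.** The strongest reply is that this is a reasonable burden choice. Centres join voluntarily and without payment (section 3.1), the data come from routine care, and hourly sampling is defensible. The main settings are not lost in short cases, because the weaning record repeats them twice. The reading at the beginning of weaning may even show the closing maintenance settings, since that moment is not defined. All of this stands, and it confines the point to the items that the weaning record leaves out.

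Two stronger readings are tempting. A reader might infer that all ventilator settings are seen only at induction and hourly. The weaning record contradicts that for mode, tidal volume, applied PEEP, FiO2 and respiratory rate.

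A reader might also infer that every ventilation summary becomes a function of case duration, so that the association in section 2.1 ("The key mechanical ventilator regulations during general anesthesia for surgery are independently associated with PPCs incidence") is biased. The documents do not support this. It would follow for a per-patient mean or maximum over all readings, but not for reporting by time point or for an induction-only summary. The protocol fixes no within-patient summary, and that choice may properly sit in the analysis plan. Durations of anaesthesia and surgery are recorded, and section 6 commits to confounder adjustment. No size for such a bias can be derived from the documents, which give neither case lengths nor differences between induction and maintenance values.

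The reply does not cover the missing values. Adjustment and choice of summary work on recorded readings. Neither supplies an in-surgery pressure or compliance for a patient who has none.

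**Conclusion.** The point holds in a narrow form. In cases that end before the first hourly mark, peak, plateau and mean airway pressure, I/E ratio, total PEEP, compliance and resistance have at most the induction reading. For those patients the mechanics part of secondary endpoint 1 has no maintenance value, and any use of mechanics in the open versus minimally invasive comparison would rest on induction values.

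This assumes that the hourly clock runs from induction and that positioning and insufflation usually come after the induction reading. The share of patients affected cannot be computed from the documents. The primary endpoint, the sample size and the capture of intraoperative adverse events are not touched. This is an inexpensive improvement to data collection. It is not an error or contradiction in the plan.

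**What to change.** In section 5.2, add for every case one reading of the full hourly item set at a defined maintenance point, for example the last reading before weaning starts. Report induction and maintenance readings separately for secondary endpoint 1, and use the maintenance reading where mechanics are compared between open and minimally invasive surgery.

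The cost is one more set of routine monitor values to enter per patient and one sentence on reporting. A case under one hour would then have two full-set readings instead of one. The change has to be made before a hospital's collection week. For data already collected, the remaining option is to label mechanics from cases under one hour as induction values and to state how many such cases there are.

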2.2. Study objectives

- To describe the incidence and type of PPCs in the first 5 postoperative days;
- To describe associations of patient, surgery, and intraoperative ventilation characteristics with the occurrence of PPCs;
- To describe the impact of intraoperative hemodynamic management on the occurrence of PPCs;
- To describe the occurrence of intraoperative adverse events (IAEs); and
- To describe geo
 economic differences in intraoperative ventilation management.

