11.2. IAEs definition

IAEs include episodes of hypoxia (SpO2<92%), use of unplanned lung recruitment maneuvers (ventilation strategies aimed to restore aeration of the lungs); airway pressure reduction (ventilation strategies aimed to lower peak and plateau pressure), presence of expiratory flow limitation (expiratory flow higher than zero at end-expiration as suggested by visual analysis of the expiratory gas flow curve), use of vasoactive drugs (any given to correct hypotension), and new arrhythmias (atrial fibrillation, sustained ventricular tachycardia, supraventricular tachycardia, or ventricular fibrillation).

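### Endpoint 4 asks for the impact of hemodynamic management on PPCs, but blood loss is not collected, so the fluid and transfusion part is likely to be confounded by bleeding and only partly adjustable

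*Protocol*

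**What the plan says.** Protocol 2.2 sets the objective "To describe the impact of intraoperative hemodynamic management on the occurrence of PPCs", and 5.1.2 repeats it as secondary endpoint 4: "describing the impact of intraoperative hemodynamic management on the occurrence of PPCs".

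The data that bear on it are in 5.2 and 11.2:

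- **Whole-case treatment totals** (5.2, peri-operative variables): "total intra-operative fluid and total transfusion of blood products, temperature and hemoglobin at end of surgery (if clinically available".
- **Monitoring** at induction and hourly (5.2, day 0): "mean, systolic, and diastolic arterial pressure (either invasive or non-invasive) (mmHg", with heart rate in the same list.
- **Vasoactive drugs**, as an intraoperative adverse event (11.2): "use of vasoactive drugs (any given to correct hypotension".
- **Possible proxies for bleeding** (5.2): urgency, "planned duration of surgery, type of surgical procedure, and surgical technique", actual durations of surgery and anesthesia, and "preoperative biochemical exams", in which hemoglobin is not named.

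Neither 5.2 nor 11.2 lists intraoperative blood loss or urine output. Urine appears only as oliguria in the postoperative kidney injury definition (11.3). Section 5.2 treats its listed items as what makes a record complete.

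Section 6 plans logistic regression for PPCs and adds: "These analyses will be adjusted for potential confounders identified at the study's outset". That sentence follows the models on patient characteristics and names no confounders.

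**The concern.** Fluid and blood products are given in large part because the patient bleeds. Bleeding is also plausibly tied to the extent of surgery, to hypotension and to PPC risk. If it is not recorded, a comparison of PPC rates by fluid or transfusion volume mixes the treatment with the reason for it. The expected direction of the error is a harmful-looking association.

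A statistical analysis plan cannot mend this, because it can choose covariates only from what was collected. Retrieval from charts also has an end date: under 8.1 the link between record and patient is destroyed when monitoring ends.

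The word *impact* makes the gap matter more. A reader will take it as a statement about what the treatment does, and the registry has stated an interest in informing later randomized trials (1.2).

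**Working it through.** **The plan's own figure.** Section 4.4 gives 10% PPCs, n = 10,000 and a Clopper-Pearson interval width of 0.0119. With 1,000 events in 10,000 the limits are 0.09419 and 0.10605, a width of 0.01186, so the figure reproduces. The point does not depend on it; only the 10% and the 10,000 are carried forward.

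**Model 1: fluid as a continuous exposure.** The documents give no bleeding figures, so everything except 10% and 10,000 is assumed. Let B be blood loss and F total fluid, both in SD units, with correlation ρ. Let logit P(PPC) = a + βB, with no F term, so the true OR for fluid is 1. Three scenarios are used: (β, ρ) = (0.3, 0.4), (0.5, 0.5), (0.7, 0.6).

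To first order, the log OR that appears for F is β × c, where c is the coefficient of F when B is regressed on F and the other covariates:

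- No covariates: c = ρ.
- A proxy explaining 50% of the variance of B (0.5/0.5 = 1): c = [ρ/(1−ρ²)] / [1 + 1 + ρ²/(1−ρ²)].
- That proxy plus estimated blood loss with reliability 0.7 (0.7/0.3 = 2.333): c = [ρ/(1−ρ²)] / [1 + 1 + 2.333 + ρ²/(1−ρ²)].

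Errors in F, the proxy and the estimate are taken as independent given B. For ρ = 0.5, ρ/(1−ρ²) = 0.6667 and ρ²/(1−ρ²) = 0.3333. So c = 0.5, then 0.6667/2.3333 = 0.2857, then 0.6667/4.6667 = 0.1429. Times β = 0.5 these give log ORs of 0.25, 0.1429 and 0.0714.

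| (β, ρ) | Unadjusted: β×c, OR | Proxy: β×c, OR | Proxy + estimated blood loss: β×c, OR |
|---|---|---|---|
| (0.3, 0.4) | 0.120, 1.13 | 0.0652, 1.07 | 0.0316, 1.03 |
| (0.5, 0.5) | 0.250, 1.28 | 0.1429, 1.15 | 0.0714, 1.07 |
| (0.7, 0.6) | 0.420, 1.52 | 0.2561, 1.29 | 0.1340, 1.14 |

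Fitting the logistic models to a large simulated population gives the same values, except 1.50 in place of 1.52, where the first-order formula is slightly high. A separate simulation of the same model gave 1.13 to 1.50, 1.07 to 1.28 and 1.04 to 1.15, which agrees to within 0.01. The z values at n = 10,000 from the fitted models are:

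- unadjusted: 3.6, 7.3, 11.9
- with the proxy: 1.9, 3.9, 6.7
- with the proxy and estimated blood loss: 0.9, 1.9, 3.3

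Adding estimated blood loss cuts the remaining log OR to 0.0316/0.0652 = 48%, 50% and 52% of its size. With a poorer estimate (reliability 0.5, so 2.333 becomes 1), β×c is 0.0448, 0.100 and 0.184. The ORs are then 1.05, 1.11 and 1.20, and the reduction is about 30%.

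**Model 2: transfusion as yes/no.** Assumed: true transfusion OR 1, major bleeding in 5% or 10% of patients, bleeding-PPC OR of 1.5, 2 or 3, and transfusion in 30% or 50% of bleeders and 3% of others. That makes 12 scenarios. The most extreme is 10%, OR 3 and 50%:

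- PPC risk is 0.0865 without and 0.2213 with bleeding, which averages to 10%.
- Transfused: 0.10×0.5 + 0.90×0.03 = 0.077. Bleeders make up 0.05/0.077 = 0.649 of the transfused and 0.05/0.923 = 0.054 of the rest.
- PPC risk is 0.174 if transfused and 0.094 if not, so the apparent OR is 2.03 (95% CI 1.67 to 2.48 at n = 10,000).

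Over the 12 scenarios the apparent OR runs from 1.15 to 2.03. The CI excludes 1 in 8 and includes it in 4. Stratifying on a proxy with sensitivity 0.7 and specificity 0.9 leaves 1.12 to 1.76.

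**The case against.** The strongest reply has five parts.

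1. **Hemodynamic management is wider than fluid and blood.** Pressure and heart rate are recorded hourly, and vasoactive use is recorded as an adverse event. This stands: the defect touches part of one secondary endpoint. Vasoactive drugs given for bleeding-related hypotension may share the confounder, but the exposure is at least captured.
2. **Proxies exist.** This stands in part. Procedure type, urgency, technique and planned duration describe expected bleeding rather than what happened. End-of-surgery hemoglobin is conditional, and it is altered by the fluid and blood given, as pressure and heart rate are. Both models show a smaller bias after proxy adjustment, not its absence.
3. **Blood loss is itself an imprecise estimate.** This stands. An adjusted OR of exactly 1 would need error-free blood loss. Whole-case blood loss also accrues while treatment is being given, so one total cannot settle time order.
4. **The verb is to describe, in an observational registry.** This stands as far as it goes. An association reported with its limits would not be wrong; *impact* is the word that goes too far.
5. **Urine output is not a measure of bleeding.** This stands. Its absence limits fluid balance, not the adjustment discussed here.

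A reader might infer that fluid and transfusion are bound to appear to cause PPCs, or that no model could reduce the problem. The documents support neither. They give no figures for bleeding, the proxies allow partial adjustment, and in 4 of the 12 transfusion scenarios the interval includes 1.

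**Conclusion.** The point holds for the fluid and transfusion part of secondary endpoint 4 and its objective. The plan stores the treatments but not a main reason for giving them, and words the result as an impact. Confounding by bleeding is likely and can be only partly removed with what is collected.

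On the assumptions above, a fluid effect that does not exist would show as an OR per SD of about 1.13 to 1.50 unadjusted and 1.07 to 1.29 with a good proxy. Recording estimated blood loss would bring this to about 1.03 to 1.14, roughly half of the remaining log OR. These figures show the order of the problem and do not predict it. In the middle and upper scenarios the proxy-adjusted result would still pass the 0.05 threshold of section 6 at n = 10,000; in the lowest it would not (z = 1.9).

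The primary endpoint and the sample size are unaffected.

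**What to change.** - Add estimated intraoperative blood loss (ml) to the peri-operative variables in 5.2.
- State that fluid and transfusion analyses for endpoint 4 are adjusted for it together with weight, duration and surgical characteristics.
- In 2.2 and 5.1.2, replace *impact* with *association*, and state that residual confounding by bleeding remains.
- Urine output is optional. It would allow a fluid balance to be formed and does nothing for confounding by bleeding.

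If the field cannot be added, the rewording and the stated limitation should still be made.

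The cost is one extra field, usually available on the anesthetic chart, and two changes of wording. The drawback is that blood loss is estimated with error, so the adjustment is incomplete and must be reported as such. The field has to be in the eCRF before centers collect data, or at the latest before the patient link is destroyed.
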